5.3.2 Methods of sample collection

For quantification of analyte plasma concentrations, blood will be taken from an antecubital or forearm vein, at the times indicated in the [Flow chart](#). Blood will be withdrawn by means of single-time venipuncture.

Details on sample characteristics, collection, processing, handling and shipment are provided in the Laboratory Manual in the ISF.

Samples will be stored in a freezer at the analytical laboratory until finalization of the clinical trial report (CTR). The plasma samples may be used for further methodological investigations (e.g. for stability testing). However, only data related to the analyte will be generated by these additional investigations. The study samples will be discarded after completion of the additional investigations according to local legislation, but not later than at the time of completion of the CTR.

5.4 ASSESSMENT OF BIOMARKERS

No exploratory biomarkers are planned. Established biomarkers of efficacy and safety are described and discussed in [Section 5.1](#) and [Section 5.2](#).

5.5 BIOBANKING

Not applicable.

5.6 OTHER ASSESSMENTS

Not applicable.

5.7 APPROPRIATENESS OF MEASUREMENTS

The primary endpoint measurements will be consistent with the recognized standard for ARDS in the setting of COVID-19 to assess treatment effects, including the clinical functional status.

All secondary [REDACTED] measurements performed during this trial are standard measurements and will be performed in order to determine the efficacy and safety in an appropriate way. The planned measurements are appropriate to see drug-induced changes in vital signs, functional parameters, standard laboratory values and coagulation parameters specific to efficacy and safety of the study drug. The endpoints are widely used and accepted for evaluation of efficacy and safety on an intravenously applied drug in a hospital setting.

Therefore, the appropriateness of all measurements applied in this trial is given.

6. INVESTIGATIONAL PLAN

The trial consists of three periods, a screening period, an intravenous open-label treatment period and a follow-up period.

During the treatment period, patients will receive an open-label infusion with alteplase on top of SOC, or SOC alone.

Instructions on alteplase infusion dosage and treatment schedule is provided in [Table 4.1.4:1](#).

All required procedures are described in the [Flow chart](#) and [Section 5](#).

After completion of the treatment period patients will be followed-up on Day 6, Day 7, Day 28 and Day 90/EOS.

If patient is discharged from hospital before completion of Day 28, the patient has to be invited to complete subsequent visits as per [Flow chart](#) until Day 90 including vital status collection.

6.1 VISIT SCHEDULE

No study procedures may be initiated prior to the patient or patient's legally acceptable representative signing the informed consent. A patient who could not provide informed consent at the start of the trial due to the severity of the disease, may have their legally acceptable representative to sign the consent on their behalf, in accordance with applicable laws and regulations. Once patient is recovered, they would need to provide their own consent to continue in the study.

An independent witness may be required in the event that the patient is able to give verbal consent, but unable to sign the consent form. Please refer to [Section 8.1](#) for more details on consenting process.

During the Screening Visit at any time of the day or night, eligible patients who are exhibiting signs and symptoms of COVID-19 induced ARDS may be asked to participate in the study.

Patients fulfilling all eligibility criteria will be randomised to one of three treatment arms in Part 1, and to one of two treatment arms in Part 2.

For potential modification of trial conduct in case of restrictions due to COVID-19, please refer to [Appendix 10.4](#).

6.2 DETAILS OF TRIAL PROCEDURES AT SELECTED VISITS

Study procedures to be performed at each visit are listed in the [Flow chart](#) and the respective protocol Sections.

6.2.1 Screening and run-in periods

Screening Period

Once the patient has consented, the patient is considered to be enrolled in the trial. The patient should be recorded on the enrollment log and be registered in the IRT.

Each patient will be assigned a unique patient number and enrollment will be recorded in eCRF.

For the schedule of assessments and procedures during the screening period refer to the [Flow Chart](#).

Laboratory samples shall be collected as per [Table 5.2.3:1](#) for haematology, clinical chemistry, renal function and coagulation including urine pregnancy testing (only applicable for women of childbearing potential). Local laboratories are intended to be used for all assessments.

The qualifying $\text{PaO}_2/\text{FiO}_2$ ratio should be the worst measurement in the screening period.

For eligibility, patients should be hospitalized with the diagnosis of COVID-19 ARDS. SARS-CoV-2 laboratory confirmation (RT-PCR test) is a pre-requisite at screening. The RT-PCR test needs to be in timely association with the current hospital stay.

Re-screening

A patient may be re-screened once within same hospital stay if the patient does not fulfill eligibility criteria. In case of re-screening patient will obtain new patient number per IRT.

Run-in Period

Not applicable.

6.2.2 Treatment periods

Randomisation of patients (Day 1, Visit 2a) shall happen not later than 24 hours after the confirmation of the inclusion and exclusion criteria. Study drug dispensing and administration shall start within 6 hours of randomisation. The time-point of obtaining D-Dimer levels can be as long as four calendar days before screening.

Treatment period duration is 5 days.

Interruptions for urgent reasons for a total of up to 72 hours are allowed and accordingly, the time window of the visits may be extended.

Patients who discontinue trial treatment prematurely should still follow the trial schedule until Visit 6/EOS, if possible, please see [Section 3.3.4](#), including vital status collection.

For the schedule of assessments and procedures during the treatment period refer to the [Flow Chart](#).

Please refer to [Table 4.1.4:1](#) for Dosing and Treatment schedule and Instructions for Dose calculation and Infusion rates of Alteplase ([Appendix 10.5](#))

For details on PK sampling collection please refer to [Section 5.3.1](#).

During the treatment period the worst measurement on a given day should be documented in the case report form. During the first 6 days and during the stay on ICU (whatever is longer), PaO₂/FiO₂ ratio should be measured at least three times daily in all patients, together with a recording of the patient's position.

Assessment of time-point of intubation and extubation, or start and end of non-invasive ventilation and oxygen support is collected.

In addition to the scheduled ECGs, ECGs should be done and documented at any time of clinical event (e.g. acute event of arrhythmia, tachy- or bradycardia, angina, or MI).

6.2.3 Follow-up period and trial completion

Patients will be followed after treatment period up to Day 90. Follow-up period consists of 4 visits: Day 6, Day 7, Day 28 and Day 90/vital status collection.

For the schedule of assessments and procedures during the follow-up period refer to the [Flow Chart](#).

Vital status shall be collected for all patients at V6/EOS (see [Flow Chart](#)). Vital status can be collected by any means approved and accepted by local legislation in each individual country and does not require an on-site visit of the patient at the study site.

7. STATISTICAL METHODS AND DETERMINATION OF SAMPLE SIZE

The eligible patients for this trial will be randomised in Part 1 to one of three treatment arms

- alteplase 0.3mg/kg over 2 hours, followed by daily long-term (12h) infusion of 0.02 mg/kg/h over 5 days, “alteplase dosing regimen A”
- alteplase 0.6mg/kg over 2 hours, followed by daily long-term (12h) infusion of 0.04 mg/kg/h over 5 days, “alteplase dosing regimen B”
- standard of care

in a 1:1:1 ratio, stratified according to ventilation (invasive mechanical vs. non-invasive).

In Part 2, patients will be randomised to

- alteplase (one dosing regimen), depending on results of Part 1. Accordingly, the following dosing regimen will be carried forward in Part 2: alteplase 0.6mg/kg over 2 hours, followed by daily long-term (12h) infusion of 0.04 mg/kg/h over 5 days, “alteplase dosing regimen B”
- standard of care

in a 2:1 ratio, stratified according to baseline ventilation status (invasive mechanical vs. non-invasive) and baseline D-Dimer level (\geq ULN to <5 vs \geq 5-fold ULN).

Throughout this whole Section, the NIV (non-invasive ventilation) patient cohort are those with a baseline WHO value of 6, and the IMV (invasive mechanical ventilation) patient cohort are those with a value 7, 8 or 9 at baseline.

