3. DESCRIPTION OF DESIGN AND TRIAL POPULATION

3.1 OVERALL TRIAL DESIGN

This is an open-label operationally seamless Phase IIb/III randomised, sequential, parallel-group adaptive clinical trial in patients experiencing ARDS triggered by COVID-19, comparing daily intravenous infusion of alteplase, up to a maximum treatment duration of 5 days on top of SOC, versus SOC alone. This trial will investigate the efficacy and safety of different dosing regimens in hospitalized patients with ARDS of mild to moderate severity.

The study comprises two parts in an operationally seamless sequential adaptive design: Part 1 (dose-finding, “proof of concept”, Phase IIb) with approximately 60 patients using a 1:1:1 randomisation scheme to two dose regimens of alteplase treatment on top of SOC, or SOC alone; and Part 2 (confirmatory, Phase III) with approximately 260 patients carrying one dosing regimen forward and using a 2:1 randomisation to alteplase treatment on top of SOC, or SOC alone.

The two parts include the same patient population and have same primary endpoint. Visit schedules are the same in both parts. There will be one interim assessment after Part 1.

One dosing regimen of alteplase (0.6/0.04 mg/kg dosing, see [Section 4.1.1](#)) has been selected for Part 2, based on the benefit-risk profile observed in Part 1.

To minimize the bias, eligible patients will be randomised using Interactive Response Technology (IRT). The randomisation list will be generated using a validated system, which involves a pseudo-random number generator so that the resulting treatment will be reproducible and non-predictable. The block size will be documented in the CTR. Access to the codes will be controlled and documented.

Randomisation in Part 1 will be 1:1:1 to one of the three arms:

- initial i.v. infusion of alteplase 0.3 mg/kg/2h (Day 1) followed by daily i.v. long-term infusion of 0.02 mg/kg over 12 hours (Dosing regimen A),
- initial i.v. infusion of alteplase 0.6mg/kg/2h (Day 1) followed by daily i.v. long-term infusion of 0.04 mg/kg/h over 12 hours (Dosing regimen B)
- or SOC.

Randomisation will be stratified by type of ventilation (non-invasive or invasive mechanical).

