3.3.2 Inclusion criteria

Patients participating in Part 1 are not eligible for Part 2.

1. Age \geq 18 years-(or above legal age)
2. ARDS with $\text{PaO}_2^*/\text{FiO}_2$ ratio >100 and ≤ 300 , either on non-invasive ventilator support, OR on mechanical ventilation (<48 hours since intubation),
 - with bilateral opacities in chest X-ray or CT scan (not fully explained by effusions, lobar/lung collapse, or nodules)
 - with respiratory failure (not fully explained by cardiac failure/fluid overload)

*or estimation of $\text{PaO}_2/\text{FiO}_2$ from pulse oximetry ($\text{SpO}_2/\text{FiO}_2$) (see [Appendix 10.2](#) for $\text{SpO}_2/\text{FiO}_2$ estimation)
3. SARS-CoV-2 positive (laboratory-confirmed RT PCR test)
4. Fibrinogen level \geq lower limit of normal (according to local laboratory)
5. D-Dimer \geq upper limit of normal (ULN) according to local laboratory
6. Signed and dated written informed consent in accordance with ICH Good Clinical Practice (GCP) and local legislation prior to admission to the trial.

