7.4 RANDOMISATION

BI will arrange for the randomisation and the packaging and labelling of trial medication. The randomisation list will be generated using a validated system, which involves a pseudo-random number generator so that the resulting treatment will be reproducible and non-predictable. The block size will be documented in the CTR. Access to the codes will be controlled and documented.

Randomisation in Part 1 will be to the three treatment arms of:

- alteplase 0.3mg/kg over 2 hours followed by 0.02 mg/kg/h over 12 hours “dosing regimen A”
- alteplase 0.6 mg/kg over 2 hours followed by 0.04 mg/kg/h over12 hours “dosing regimen B”
- SOC

With an allocation ratio of 1:1:1, with stratification by the following factor:

- Type of ventilation (non-invasive or invasive mechanical)

Randomisation in Part 2 will be to alteplase and to standard of care, with an allocation ratio of 2:1, with stratification by the following factors:

- Type of ventilation (non-invasive or invasive mechanical)
- D-Dimer levels (\geq ULN to <5 -fold ULN, versus ≥ 5 -fold ULN)

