7.4 PRIMARY ENDPOINT(S)

7.4.1 Primary analysis of the primary endpoint(s)

For the primary endpoint, a cox proportional hazards model will be used to estimate the hazard ratio (HR) comparing the alteplase groups to SOC. From the model, the 95% confidence intervals (CI) and corresponding Wald p-values for the HRs will be produced. The model will include fixed effects for treatment (alteplase group of interest, SOC), the randomisation stratification factor type of ventilation (NIV, MV) and age (continuous).

Baseline ventilation status (NIV/MV) and baseline status on the WHO eleven-point clinical progression scale (5, 6, 7, 8 or 9) are correlated. That is to say, NIV take on values of 5 and 6, whilst MV takes on values of 7, 8 and 9 on the WHO clinical progression scale. Of these two, only the randomisation stratification factor ventilation status will be used in the primary model to avoid over parameterising. This is not considered to be a change from the CTP, since this still includes the baseline WHO status.

Kaplan Meier estimates will be presented by treatment (low alteplase, high alteplase, SOC) for this endpoint up to Day 28, and additionally by:

- treatment and type of ventilation (NIV, MV)
- treatment and baseline status on the WHO eleven-point clinical progression scale (5, 6, 7, 8 or 9)
- treatment and age groups (<=median, >median)

From the KM estimates stratified by treatment, and at various timepoints (days 6, 8, 12, 16, 20, 24 and 28) the risk difference (RD) with 95% CI will be estimated by taking the difference of the individual probabilities. Since the observations in the two treatment groups are independent, the variance of the Kaplan-Meier probability difference is equal to the sum of the Kaplan Meier probabilities' variances found by Greenwood's method. The 95% CI of the RD is therefore calculated accordingly.

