7. PLANNED ANALYSIS

The tables that are created from the statistical analysis will follow the format of the standard within BI [\(8\)](#).

The overall disposition of the patients in the trial will be presented, together with the number of patients discontinuing prior to day 28, and vital status at day 90.

The number of patients participating in the study by country and the number of sites, for each of the patient populations will be summarised.

Demography and baseline characteristics will be presented, as well as the stratification used at the time of the patient randomisation. A summary of the iPDs will be provided.

Where statistical comparisons are indicated, they will be done by comparing alteplase versus SOC.

All descriptive analyses will be performed:

- within the NIV patient cohort as the main cohort
- within the IMV patient cohort as the exploratory cohort
- on the NIV and IMV cohorts pooled – additional select efficacy analyses for primary and secondary efficacy endpoints

For the NIV patient cohort, the default set of covariates for adjustment in analyses are:

- Baseline D-Dimer status (≥ 3 to < 5 , ≥ 5 -fold ULN)
- Age
- Number of days of NIV support
- Baseline value of the $\text{PaO}_2/\text{FiO}_2$ ratio – only for the endpoint $\text{PaO}_2/\text{FiO}_2$ ratio change from baseline to Day 6

For the IMV patient cohort, the default set of covariates for adjustment in analyses are:

- Baseline D-Dimer status (≥ 3 to < 5 , ≥ 5 -fold ULN)
- Age
- Baseline WHO value (7, 8, 9)
- Baseline value of the $\text{PaO}_2/\text{FiO}_2$ ratio – only for the endpoint $\text{PaO}_2/\text{FiO}_2$ ratio change from baseline to Day 6

For efficacy analyses, patients will be analysed according to the patient information given in the CRF, in the case of potentially erroneous data entered into the interactive response technology (IRT). This is related to the baseline information, ventilation support (NIV, IMV) and D-Dimer level (≥ 3 to < 5 , ≥ 5 -fold ULN).

In general, for End-Of-Text tables, the set of summary statistics is: N (number of patients with non-missing values) / Mean / SD / standard error (SE) / Min / Q1 (lower quartile) / Median / Q3 (upper quartile) / Max.

Statistical parameters will be displayed to a defined number of decimal places as specified in the BI guideline "Reporting of Clinical Trials and Project Summaries" [\(9\)](#).

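### The Part 2 NIV cohort is defined as baseline WHO 6, while randomisation, stopping and the SAP's CRF rule use ventilation type, so a patient randomised as NIV with baseline WHO 5 has no settled place in the analysis

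*Protocol*

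**What the plan says.** **Cohorts by WHO score.** Protocol Section 7 states that the NIV "patient cohort are those with a baseline WHO value of 6" and that the IMV "patient cohort are those with a value 7, 8 or 9 at baseline". Part 2 SAP Section 3 repeats this. Neither assigns a score of 5.

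**Everything else by ventilation type.** Protocol Section 7.4 stratifies Part 2 by "Type of ventilation (non-invasive or invasive mechanical"). The cap of 50 IMV patients and the end of recruitment at about 210 NIV patients (Protocol Section 3.1) use the same split. Inclusion criterion 2 (Protocol Section 3.3.2) asks for patients "either on non-invasive ventilator support, OR on mechanical ventilation (<48 hours since intubation") and sets no WHO score.

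**CRF rule.** Part 2 SAP Section 7 gives CRF data precedence over IRT entries for efficacy: "This is related to the baseline information, ventilation support (NIV, IMV) and D-Dimer level". Section 7.1 repeats the rule.

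**Part 1.** Part 1 SAP Sections 4 and 7.4.1 say that "NIV take on values of 5 and 6, whilst MV takes on values of 7, 8 and 9", and Section 7.4.1 plans Kaplan-Meier curves for baseline WHO 5. Protocol Section 3.1 says: "The two parts include the same patient population and have same primary endpoint".

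**Scope.** Protocol Section 7.2.1 runs all analyses, including safety, within the two cohorts. The Part 2 SAP adds only the two cohorts pooled. Protocol Section 7.2.5 nevertheless promises that every treated patient enters the safety analysis.

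**The concern.** The set of patients randomised, counted and used to end recruitment is not, as worded, the set that is analysed. A patient in the NIV stratum with baseline WHO 5 helps close recruitment. On the WHO definition, that patient is then absent from the primary test, both key secondary tests, the IMV cohort, the pool of the two cohorts and the major-bleeding analysis. On the CRF rule the same patient is in the confirmatory NIV cohort. The FAS has no WHO restriction, so it does not decide between the two.

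Membership of the confirmatory set should not need a decision after data accrue. This matters more here because the trial is open-label and individual treatment is in the database after randomisation (Part 2 SAP Section 8.1).

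**Working it through.** **1. Can a WHO 5 patient be in the NIV stratum?** Protocol Section 5.1.1 scores NIV or high-flow oxygen as 6, and mask or nasal prongs as 5. The baseline score is taken just before randomisation. Randomisation may follow confirmation of eligibility by up to 24 hours (Protocol Section 6.2.2), so a step-down in support in that interval gives a score of 5. The stratification factor has two levels, and a patient who is not intubated fits only the non-invasive one. The Part 1 SAP lists 5 among the NIV values. When its second version revisited the baseline values to accept WHO 9, it kept the 5. The possibility is real; its frequency is not stated.

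**2. Where does that patient go?**

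| Rule | Source | WHO 5 patient |
|---|---|---|
| Stratum and count to 210 | Protocol 3.1, 7.4 | NIV |
| Cohort by WHO score | Protocol 7; Part 2 SAP 3 | neither cohort |
| CRF ventilation support | Part 2 SAP 7, 7.1 | NIV |
| FAS, TS | Protocol 7.2.1; Part 2 SAP 6.3 | in, if the other conditions are met |
| Safety analysis | Protocol 7.2.5 | in, if treated |
| Safety by cohort and pool | Protocol 7.2.1; Part 2 SAP 7.8 | out, on the WHO definition |

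**3. Stated power, reproduced.** Inputs from Protocol Section 7.5: 140 and 70 patients, two-sided 5%; HR 2.0 with event rates 50% and 30%; treatment failure 20% and 40%; mortality 9% and 25% (alteplase and SOC respectively).

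H0_1 (Schoenfeld):
- Events d = 0.30 × 70 + 0.50 × 140 = 91.
- Power = Φ(√(d × 2/3 × 1/3) × ln 2 − 1.96) = Φ(4.497 × 0.693 − 1.96) = Φ(1.157) = 87.6%.

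H0_2 and H0_3 (two proportions, pooled variance under the null): power = Φ((|difference| − 1.96 × SE0) / SE1).
- H0_2: pooled rate (28 + 28)/210 = 0.267, SE0 = 0.0647, SE1 = 0.0676; Φ((0.20 − 0.1269)/0.0676) = 86.0%.
- H0_3: pooled rate (17.5 + 12.6)/210 = 0.143, SE0 = 0.0513, SE1 = 0.0571; Φ((0.16 − 0.1005)/0.0571) = 85.1%.

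These match the stated 85% to 90% for the first two tests and 85% for the third. The protocol does not name its formula; the pooled form is used because it reproduces the stated figures.

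**4. Power if a share is WHO 5 and left out.** The share is an assumption. Patients are removed equally from both arms, with event rates unchanged.

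| Assumed share | NIV patients analysed | Events | H0_1 | H0_2 | H0_3 |
|---|---|---|---|---|---|
| 0% | 210 | 91.0 | 87.6% | 86.0% | 85.1% |
| 2% | about 206 | 89.2 | 87.0% | 85.4% | 84.4% |
| 5% | about 200 | 86.5 | 86.0% | 84.3% | 83.4% |
| 10% | 189 | 81.9 | 84.1% | 82.4% | 81.5% |

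**5. Margin.** H0_1 needs 85 events for 85% power. At the planned event fraction of 91/210 = 0.433, that is 85/0.433, or about 196 patients. H0_1 therefore falls below 85% only if more than about 14 of the 210 (14/210 = 6.7%) are lost. H0_2 and H0_3 have almost no margin.

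**The case against.** The case for leaving the text alone has real force.

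- **WHO 5 should rarely occur.** Criterion 2 requires non-invasive ventilator support, which the scale scores as 6. Read strictly, the stratum and the cohort nearly coincide. This stands and limits the size of the problem.
- **The Part 1 SAP is weak evidence.** It is limited to Part 1, lists possible values and reports no count at WHO 5. Both Part 2 documents say 6. This stands as to frequency, but it does not remove the conflict inside the Part 2 documents.
- **The CRF rule already helps.** It does, but it is written to correct IRT entry errors and does not say that it overrides the WHO definition.
- **WHO 6 is a homogeneous population.** From 6, a two-point improvement means 4, in hospital without oxygen; from 5 it means 3, an ambulatory state. The covariate for days under NIV support may also fit WHO 5 patients poorly. This is a fair cost of widening the cohort.

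A reader might infer more than the documents support, in four ways:

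- That the exclusion biases the comparison or inflates type I error. It does not: the score precedes randomisation, so the comparison within WHO 6 remains randomised.
- That taking the worst screening PaO2/FiO2 makes WHO 5 routine. That rule concerns the ratio, not ventilator support.
- That these patients vanish from the trial. They remain in disposition and, by definition, are eligible for the FAS and TS.
- That the cohort should be WHO 6 or lower. That would also admit WHO 4, patients without oxygen therapy.

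**Conclusion.** The point holds as a conflict between rules with a possible loss of precision. Two Part 2 rules place the same patient differently, and the WHO rule departs from the randomisation stratum, the 210-patient count and the commitment to include all treated patients in safety.

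The size is unknown because the documents give no count at WHO 5. On the assumptions in the working, a 5% share costs each test 1.6 to 1.7 percentage points of power and a 10% share costs 3.5 to 3.6. At 5% the primary test stays within its stated range, while both key secondary tests fall below 85%. Protocol Section 7.5 itself calls its assumptions approximate, so these losses are modest. The reason to act is that the ambiguity is cheap to remove before the data are analysed.

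**What to change.** In Protocol Section 7 and Part 2 SAP Section 3, define the NIV cohort as Part 2 patients whose baseline ventilation support on the CRF is non-invasive (baseline WHO 5 or 6, as in the Part 1 SAP), and the IMV cohort as those on invasive ventilation (WHO 7, 8 or 9). Keep the WHO 6 restriction as a sensitivity analysis of the primary and key secondary endpoints. State how the two-point improvement and the days-of-NIV covariate apply to a patient who starts at 5.

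If the sponsor does intend WHO 6 only, the documents should say so, exclude WHO 5 patients from the count of 210, and state where their safety data are reported.

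The cost is one sentence in each document plus the covariate clarification, with no new data. The downside is slightly more heterogeneity in the confirmatory cohort.
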